1.4 Enrolling personnel

At each inclusion site, all anaesthesiologists and anaesthesiologist trainees with sufficient experience to perform acute regional anaesthesia will participate in patient screening and inclusion. They will all undergo a formal introduction to ensure conformity in injection site and injected volume, prior to their inclusion of patients.

2. Introduction and background

2.1 Patient population

Each year, approximately 40.000 patients are diagnosed with a fracture in the distal forearm in Danish hospitals(1). While the term Colles' fracture is widely used to describe all the distal forearm fractures, the Danish system for encoding of diagnosis describes a variety of fracture types in the distal forearm including three fracture types of the distal radius (code DS525); the Smith fracture (DS525A), the Colles' fracture (DS525B) and the Barton's fracture (DS525C). Among all dislocated fractures of the distal forearm only the true Colles' fracture can potentially be treated adequately with a closed reduction and a cast, while the other fracture types are unstable by definition and require surgical stabilization. Most dislocated forearm fractures, however, require a primary reduction and this procedure requires the patient to be relieved of pain and the muscle traction on the fracture to be minimal.

2.2 Anaesthetic choices for distal forearm fracture reduction

The conventional method of anaesthesia for the reduction of a distal forearm fracture is the haematoma block with the local anaesthetic agent being injected directly into the fracture line. This is performed either by using a blind technique in which the physician uses the needle to feel his way across the bone surface until the fracture line is reached, or by using x-ray to visualize the needle. In either technique blood is aspirated in

the cannula as a sign of the needle tip being in the haematoma surrounding the fracture, and the local anaesthetic is injected(2,3). The haematoma block is traditionally considered to be a safe anaesthetic option even with the risk of rapid systemic absorption and a potentially toxic systemic dose of the local anaesthetic(4,5). It has never been proven superior to other techniques in systematic reviews(6,7), nor has it been compared to an ultrasound guided analgesia technique as described in the current protocol.

2.3 Innervation of the forearm and wrist

The radial and median nerves innervate the majority of muscles in the forearm and the periosteum of the ulna and radius as the posterior and anterior interosseous nerves, respectively. Therefore, blocking of these nerves at the level of the cubital fossa should alleviate pain and decrease muscular traction allowing manipulation of fractures in the radius and ulna(8,9).

2.4 Distal nerve blocks for procedures on the forearm and hand

Although blocking the radial, median, and ulnar nerves is not a commonly used form of anaesthesia for closed reduction of forearm fractures, it is by no means an experimental anaesthetic procedure. The distal nerve blocks of the forearm have long been used both as rescue blocks in case of failed infraclavicular and supraclavicular blocks and as a primary choice in the case of surgical procedures involving one or more of the nerves innervation areas(10).

2.5 Properties of lidocaine

In the present study, lidocaine is our choice of local anaesthetic as it is well-known and widely used. Lidocaine and adrenaline in combination has been approved for medical use in Denmark for decades specifically for the indications of local infiltration and nerve analgesia(11). Lidocaine is a rapid onset local anaesthetic and in combination with adrenaline has an onset time of barely 10 minutes and a duration of at least 120 minutes when used for local infiltration and blocking of small nerves(12,13).

3. Hypothesis and outcome

3.1 Hypothesis

We hypothesize that ultrasound guided blocking of the radial and median nerves will improve fracture reduction satisfaction for the true Colles' fractures and improve analgesia for reduction of all fracture types compared to the standard haematoma block.

3.2 Primary outcome

Reduction satisfaction based on objective X-ray measures according to the National Guideline for Treatment of Distal Forearm Fractures. The primary outcome applies for the true Colles' fractures only.

3.3 Secondary outcomes

Will be evaluated for all included fracture types.

- Pain scores using an 11-step numeric rating scale
- Time spent in the Emergency Department
- Secondary fracture dislocation

4 Study design and conduction

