4.3 Blinding

Only the orthopaedic surgeons evaluating the control X-ray to assess the primary outcome of fracture reduction satisfaction will be blinded to randomisation.

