4.4 Data collection

In both groups, the following will be registered during the treatment period in the emergency department:

- Pain scores using an 11-step numeric rating scale (NRS) ranging from 0 (no pain) to 10 (worst pain imaginable)
 - Before local anaesthetics are given
 - During the local anaesthetic procedure
 - During reduction
- Precise amount and type of local anaesthesia used
- In plane/out of plane technique used for the ultrasound guided blocks
- Type and amount of supplementary analgesics/sedatives before and after local anaesthesia
- Fracture classification code
- Treatment plan; conservative vs. operation
- Osteoporosis yes/no
- Patients right/left hand preference
- Patient height and weight
- Any chronic use of opioids

Following casting of the fracture a control X-ray will be performed and subsequently evaluated independently by two skilled orthopaedic surgeons to establish if the reduction was satisfactory. In case of disputes a third orthopaedic surgeon will evaluate the X-ray and make a final ruling. The orthopaedic surgeons will further determine fracture type.

In cases where more than one control X-ray is performed due to re-manipulation of the fracture, only the first will be evaluated. The fracture will be deemed satisfactory using a binary outcome measure (yes/no) if all the following requirements set by the National Clinical Guideline for Treatment of Distal Radius Fractures(14) are met:

- < 10-degree dorsal angulation of the radial articular surface
- Ulnar variance < 2 mm
- Discontinuation of the articular line < 2 mm
- No incongruence of the distal radioulnar joint

Two months after the initial treatment the electronic journal will be evaluated to establish the occurrence of secondary dislocation and need for surgery.

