4.6 Data analysis

4.6.1 Sample size estimation

The number of included patients is calculated using data from an unpublished quality database at Viborg Regional Hospital. Approximately 15 percent of the true Colles' fractures are currently being satisfactorily reduced, and we consider an increase to 30 percent to be clinically relevant. With $\alpha = 0.05$ and $\beta = 0.8$, 121 patients are needed in each group to detect a statistically significant difference in reduction satisfaction. From the same local database we found that the true Colles' fracture comprises approximately 90 % of the total number of fractures and we anticipate a total inclusion of 268 patients ($2 \times 121 + 10\%$).

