4.6.2 Statistics

Binary data, including primary endpoint will be analysed using chi squared test. For normally distributed measurements the differences between groups will be compared using Student's *t*-test. Variables considered not to be normally distributed will be analysed by Mann-Whitney's *U*-test. Two-tailed *P*-values < 0.05 will be considered statistically significant.

5. Ethical concerns

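### Does secondary fracture dislocation need a written event rule for patients with an unsatisfactory first reduction or an operation?

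*Combined protocol and SAP*

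**What the plan says.** Section 3.3 names "Secondary fracture dislocation" among the secondary outcomes and says of all of them: "Will be evaluated for all included fracture types". It gives no radiographic threshold and no reference film.

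Section 4.4 gives the source: "Two months after the initial treatment the electronic journal will be evaluated to establish the occurrence of secondary dislocation and need for surgery". The emergency department sheet also records "Treatment plan; conservative vs. operation". The four radiographic criteria in 4.4 define a satisfactory reduction for the primary outcome and are applied to the first control X-ray only, even when the fracture is re-manipulated and filmed again.

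Section 4.6.2 gives the analysis: "Binary data, including primary endpoint will be analysed using chi squared test". Section 4.3 limits blinding: "Only the orthopaedic surgeons evaluating the control X-ray to assess the primary outcome of fracture reduction satisfaction will be blinded to randomisation". The planning figures are in 4.6.1: "Approximately 15 percent of the true Colles' fractures are currently being satisfactorily reduced, and we consider an increase to 30 percent". Section 2.1 says of fractures other than the true Colles' that "the other fracture types are unstable by definition and require surgical stabilization".

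**The concern.** To dislocate secondarily, a fracture must first have been in some position that can be lost. If that position has to be a satisfactory one, most patients in this trial start outside the risk set, and the treatment is meant to change who is in it. A block that improves reduction would then show more dislocations than control only because more of its patients had something to lose. If any later loss of position counts, the same block would show fewer dislocations or no difference. The sign of the estimate would depend on an unstated choice, made at an unblinded journal review.

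Operated patients raise a second question. Someone operated before any dislocation is recorded would count as having no event. If that happens more often after poor reductions, the difference between arms shrinks. Need for surgery is collected at the same review but is not listed in 3.3, so it could go unreported.

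**Working it through.** **Inputs from the plan (4.6.1).** Satisfactory reduction is 15% in control and 30% in intervention, with 121 true Colles' fractures per arm. True Colles' fractures are about 90% of the total. The documents give no dislocation, re-manipulation or surgery rates, so every such rate below is an assumption, taken as equal in both arms. Differences are intervention minus control.

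**The plan's own figure.** Two proportions, two-sided 5%, pooled variance, power read as 0.80 (4.6.1 writes this as beta), no continuity correction:

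n = [1.96 × √(2 × 0.225 × 0.775) + 0.8416 × √(0.15 × 0.85 + 0.30 × 0.70)]² / 0.15² = (1.157 + 0.489)² / 0.0225 ≈ 120.5, so 121 per arm, as stated. The total of 268 is close to 242/0.9 = 268.9.

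**Unsatisfactory first X-rays.** 1 − 0.15 = 85% and 1 − 0.30 = 70%, or about 103 and 85 of 121. The 70% is the target effect, not an observed rate.

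**Reading A: only a satisfactory position can be lost.** With no successful re-manipulation, 0.15 × 121 ≈ 18 and 0.30 × 121 ≈ 36 patients are at risk, a ratio of 2.0. At a 20% dislocation risk, control has 0.15 × 0.20 = 3.0% and intervention 0.30 × 0.20 = 6.0%, a difference of +3.0 points.

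Section 4.4 foresees re-manipulation. If a share r of unsatisfactory first reductions is later made satisfactory, the shares at risk are 0.15 + 0.85r and 0.30 + 0.70r:

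| r | Control | Intervention | Ratio | Difference at 20% risk |
|---|---|---|---|---|
| 0 | 15% | 30% | 2.0 | +3.0 points |
| 0.2 | 32% | 44% | 1.38 | 0.20 × 12 = +2.4 points |
| 0.5 | 57.5% | 65% | 1.13 | 0.20 × 7.5 = +1.5 points |

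The ratio of 2.0 is therefore the extreme of Reading A.

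**Reading B: any included patient can have the event.** With risk 20% after a satisfactory and 40% after an unsatisfactory reduction:

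- control: 0.15 × 0.20 + 0.85 × 0.40 = 37.0%
- intervention: 0.30 × 0.20 + 0.70 × 0.40 = 34.0%
- difference: −3.0 points

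At 10% and 40% the difference is 0.15 × (0.10 − 0.40) = −4.5 points. If the two risks are equal it is 0. Adding the 10% of other fractures, with no difference between arms among them, multiplies by 0.9 (−3.0 becomes −2.7).

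**Surgery under Reading B.** Let s be the share of unsatisfactory reductions operated and f the share of their dislocation risk recorded before surgery, with no surgery after a satisfactory reduction. The difference is 0.15 × [0.20 − 0.40 × (1 − s(1 − f))].

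| s | f = 0 | f = 0.5 | f = 1 |
|---|---|---|---|
| 0.10 | −2.4 | −2.7 | −3.0 |
| 0.25 | −1.5 | −2.25 | −3.0 |
| 0.50 | 0 | −1.5 | −3.0 |

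The attenuation comes wholly from the assumed s and f. If surgery follows a recorded dislocation, there is none.

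**Precision at 121 per arm.** The 95% half-width is 1.96 × √[(0.03 × 0.97 + 0.06 × 0.94)/121] = 5.2 points for 3% against 6%, and 1.96 × √[(0.37 × 0.63 + 0.34 × 0.66)/121] = 12.1 points for 37% against 34%. Power is about 20% and 8%.

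**Which reading the text supports.** Section 3.3 applies the secondary outcomes to every included fracture type. The satisfactory/unsatisfactory criteria in 4.4 serve the primary outcome, which 3.2 limits to true Colles' fractures. No section links dislocation to a satisfactory first X-ray. Reading B is the plain one, and it does not turn the sign against the block unless the risk after a satisfactory reduction exceeds the risk after an unsatisfactory one, or enough surgery comes before dislocation.

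**The case for a change.** The best case for a change is that the open question covers most patients: about 188 of the 242 planned true Colles' fractures (103 + 85) have an unsatisfactory first X-ray, and the treatment is meant to alter that number. At assumed risks of 20% and 40%, moving from one reading to the other takes the expected difference from −3.0 to +3.0 points. The journal review is unblinded, and a sentence of text costs nothing.

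Some of this stands. The outcome has no threshold or reference film for any patient, the two-month classification is not blinded, and 3.3 does not list need for surgery. The reversal, however, needs a restriction that the plan nowhere makes, and it weakens once re-manipulation is allowed for.

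A sentence saying that any included patient can have the event, with all included patients as the denominator, would record what analysts following 3.3 and 4.6.2 would do anyway. It would supply neither a threshold nor blinding. Surgery is binary and collected, and the chi-squared rule in 4.6.2 covers binary data without limiting itself to listed outcomes, so a comparison by arm is not ruled out.

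**Conclusion.** The definition is missing, but this is a gap that analysts fill sensibly: a dislocation recorded in the journal by two months, in any included patient, over all included patients, with an operated patient counted only if a dislocation was recorded. Under that rule the illustrated effect of the open points is at most about 3 points (−3.0 moving to 0 when half of unsatisfactory reductions are operated, all before dislocation). That is small beside a half-width of about 12 points on an outcome the trial was not sized for. The doubling of patients at risk belongs to a reading without support in the text, and only with no successful re-manipulation.

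These sizes rest on assumed dislocation, re-manipulation and surgery rates that are equal in both arms, and on the target of 30% being reached. The primary outcome, its blinded assessment and the sample size are unaffected. The trial report should say how dislocation was identified and give the surgery counts beside it; the plan need not change for that.

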4.1 Selection and enrolment of participants

4.1.1 Recruitment strategy and screening

Patients eligible for screening for inclusion are identified in the Emergency Department (ED) at all recruitment sites upon primary contact. When an X-ray has revealed the relevant fracture, the ED-staff will call the available anaesthesiologist or anaesthesiologist trainee who will perform the inclusion process and randomisation. In cases where the anaesthesiologist is unable to perform inclusion due to e.g. lack of time or experience a registration of patient data, date and time as well as the reason for the missed inclusion will be made.

In case of randomisation to the control group, the anaesthesiologist/anaesthesiologist trainee will leave the ED and take no further part in the treatment or data registration. In case of randomisation to the intervention group the anaesthesiologist/anaesthesiologist trainee will perform the ultrasound guided blocks and leave the ED before the reduction procedure begins.

For all included patients a note will be made in the electronic patient journal stating that the patient meets all in- and no exclusion criteria, has given an informed consent to participation and received a copy of the signed consent form.

4.1.2 Inclusion criteria

- Presence of a closed distal forearm fracture in need of a closed reduction
- Age > 18 years
- Legally competent

4.1.3 Exclusion criteria

- Inability to give informed consent
- Allergy or intolerance towards local anaesthetics
- Infection or burns at either injection site
- Multi trauma (defined as other fractures or significant injuries)
- Known pregnancy
- Participation in other studies

[figure not shown]
4.1.4 Information and consent

The anaesthesiologist/anaesthesiologist trainee responsible for inclusion will apply to the national regulations regarding informed consent to participation in a clinical trial. Hence, in addition to oral information the potential participant will receive written information including both the specific information on the current study as well as the general information pamphlet on participant rights when entering a clinical trial. All information and inclusion will be carried out by physicians who possess the sufficient professional prerequisites to be authorized by the sponsor to have a direct involvement in the project.

Information will be given in private and the participant will be allowed to have an assessor present. The participant will be given a brief reflection period of approximately 10 minutes before making their decision.

4.1.5 Participant flow

The following consort diagram will be continuously filled out to monitor study progress regarding primary outcome.

4.1.6 Discontinuation and withdrawal

Any participant can choose to withdraw from the study at any time. This will have no repercussions on his or her right to or quality of continuous treatment. The same applies if a discontinuation is made by the choice of the physician. In this case the patient will be informed of the reason for discontinuation. Any withdrawal or discontinuation will be noted in the consort diagram and mentioned when presenting results in future publications.

4.2 Randomisation

4.2.1 General considerations

Participants will be randomized in either the intervention or the control group using the online randomization tool Research Electronic Data Capture (REDCap, Aarhus University, Denmark).

All patients will receive an intravenous access. Monitoring of heart rate, blood pressure and oxygen saturation will be established according to local guidelines at each inclusion site before injection of local anaesthetic.

In both groups, the reduction process will begin 10 minutes after the block has been performed. The technique for the actual reduction may vary amongst physicians. To best reflect the clinical practices and to avoid the risk of an insufficient reduction due to the physician being forced to comply to a technique unfamiliar to him, no further standardisation will be made in this regard.

4.2.2 Intervention group

Using a linear probe, the medial and radial nerves will be visualized in the cubital fossa and blocked by injection of 5-7 ml lidocaine 20 mg/ml with adrenaline 5 µg/ml ('SAD').

4.2.3 Control group

Patients in the control group will receive the standard haematoma block at all inclusion sites. This will be performed using the previously described technique and local anaesthetics according to local practices.

4.3 Blinding

Only the orthopaedic surgeons evaluating the control X-ray to assess the primary outcome of fracture reduction satisfaction will be blinded to randomisation.

4.4 Data collection

In both groups, the following will be registered during the treatment period in the emergency department:

- Pain scores using an 11-step numeric rating scale (NRS) ranging from 0 (no pain) to 10 (worst pain imaginable)
 - Before local anaesthetics are given
 - During the local anaesthetic procedure
 - During reduction
- Precise amount and type of local anaesthesia used
- In plane/out of plane technique used for the ultrasound guided blocks
- Type and amount of supplementary analgesics/sedatives before and after local anaesthesia
- Fracture classification code
- Treatment plan; conservative vs. operation
- Osteoporosis yes/no
- Patients right/left hand preference
- Patient height and weight
- Any chronic use of opioids

Following casting of the fracture a control X-ray will be performed and subsequently evaluated independently by two skilled orthopaedic surgeons to establish if the reduction was satisfactory. In case of disputes a third orthopaedic surgeon will evaluate the X-ray and make a final ruling. The orthopaedic surgeons will further determine fracture type.

In cases where more than one control X-ray is performed due to re-manipulation of the fracture, only the first will be evaluated. The fracture will be deemed satisfactory using a binary outcome measure (yes/no) if all the following requirements set by the National Clinical Guideline for Treatment of Distal Radius Fractures(14) are met:

- < 10-degree dorsal angulation of the radial articular surface
- Ulnar variance < 2 mm
- Discontinuation of the articular line < 2 mm
- No incongruence of the distal radioulnar joint

Two months after the initial treatment the electronic journal will be evaluated to establish the occurrence of secondary dislocation and need for surgery.

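### Does leaving the record and film for fracture typing unstated let the reduction result decide who enters the primary Colles' comparison?

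*Combined protocol and SAP*

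**What the plan says.** Section 4.1.2 admits any closed distal forearm fracture needing closed reduction. Section 3.2 then narrows the main question: "The primary outcome applies for the true Colles' fractures only". Section 4.6.2 gives the test ("Binary data, including primary endpoint will be analysed using chi squared test") with no rule for who belongs to the Colles' set.

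Section 4.4 records fracture type twice. A list headed by the statement that "the following will be registered during the treatment period in the emergency department" includes the item "Fracture classification code". The paragraph on radiographic reading begins "Following casting of the fracture a control X-ray will be performed and subsequently evaluated independently by two skilled orthopaedic surgeons", gives a third surgeon the final ruling in disputes, and ends "The orthopaedic surgeons will further determine fracture type". No film is named for that last task.

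Section 4.3 adds: "Only the orthopaedic surgeons evaluating the control X-ray to assess the primary outcome of fracture reduction satisfaction will be blinded to randomisation". Section 4.1.1 has an X-ray reveal the fracture before the anaesthesiologist is called to include the patient, and section 5.1 seeks access to all X-ray information on the fracture.

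**The concern.** Membership of a subset analysed for the primary outcome should not depend on that outcome. Here the only film the surgeons are said to read is the control X-ray, and the typing sentence comes straight after the rating rules. Read literally, the same surgeons could type a fracture already knowing whether it was well reduced. If a poor reduction made them less willing to call it a true Colles' fracture, or a good one did, the set would be selected on the result.

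The second record adds to the worry. The emergency department code is entered by staff who are not blinded, and its timing relative to allocation, reduction and the control film is not stated. With two candidate records and no rule between them, two versions of the primary set could in principle be open at analysis. At stake are the estimated risk difference, some power and, if typing differed by arm, the false-positive rate.

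**Working it through.** **The plan's own figure.** Inputs from section 4.6.1: 15% against 30%, α = 0.05 (two-sided by section 4.6.2), power 0.80 (printed there as β = 0.8). With the pooled two-proportion formula and mean rate 0.225:

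n = [1.96·√(2·0.225·0.775) + 0.842·√(0.15·0.85 + 0.30·0.70)]² / 0.15² = (1.157 + 0.489)² / 0.0225 ≈ 120.5, so 121 per arm, as stated. Power at 121 per arm is 80.2%. With 90% true Colles' fractures, 268 × 0.90 = 241.2, or about 121 per arm. About 27 of 268 patients are expected to fall outside the set.

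**Typing that depends on the result.** Let qs be the share of successes kept in the set and qf the share of failures kept, the same in both arms because the readers do not know the allocation. For an arm with true rate p:

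- observed rate = p·qs / [p·qs + (1−p)·qf]
- arm size = 121·[p·qs + (1−p)·qf]
- observed odds = [p/(1−p)]·(qs/qf)

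The factor qs/qf cancels in the odds ratio, which stays at (0.30/0.70)/(0.15/0.85) = 2.43. If the true rates are equal, the observed rates are equal too, so the null hypothesis is preserved. One million simulated trials per setting gave rejection rates of 4.99% to 5.02% under the null.

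The documents give no relabelling rate, so those below are assumptions.

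| Typed out, both arms | Observed rates | Difference (points) | Arm sizes | Power |
|---|---|---|---|---|
| None (plan) | 15.0% v 30.0% | 15.0 | 121 v 121 | 80.2% |
| 5% of successes | 14.4% v 28.9% | 14.6 | 120.1 v 119.2 | 78.5% |
| 10% of successes | 13.7% v 27.8% | 14.1 | 119.2 v 117.4 | 76.8% |
| 20% of successes | 12.4% v 25.5% | 13.2 | 117.4 v 113.7 | 72.7% |
| 5% of failures | 15.7% v 31.1% | 15.4 | 115.9 v 116.8 | 79.7% |
| 10% of failures | 16.4% v 32.3% | 15.9 | 110.7 v 112.5 | 79.3% |
| 20% of failures | 18.1% v 34.9% | 16.8 | 100.4 v 104.1 | 78.1% |

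Losing 10% of failures would remove (121 − 110.7) + (121 − 112.5) = 18.8 further patients. Total exclusions would then be 26.8 + 18.8 = 45.6 of 268, or 17% against the expected 10%, which would be noticed. Losing 10% of successes removes only 1.8 + 3.6 = 5.4 patients and would not show in that way.

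The table covers Colles' fractures typed out. Other fractures typed in are not quantified, because the documents give no success rate for them. With blinded typing and no effect of the block on reduction in either kind of fracture, the two arms still have equal expected rates.

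**Reading the text.** An emergency department code is already on the registration sheet. A second determination by the surgeons who judge the endpoint has an obvious purpose: to settle who belongs to an endpoint limited to one fracture type. The sentence on typing names no film, so using the diagnostic X-ray is as consistent with it as using the control X-ray. Section 2.1 treats Smith, Colles' and Barton's fractures as separately coded types, whereas satisfaction in section 4.4 rests on four radiographic requirements. Nothing in the documents says that one informs the other.

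**The case for a change.** The best argument for a change is that it would cost almost nothing: the diagnostic film exists, the readers are engaged and access is sought, so the plan could name the film and the order of reading. The readers are blinded to allocation but not to the reduction result. Section 2.1 gives no radiographic criteria for a true Colles' fracture and describes it partly as the type that closed reduction and a cast may treat adequately, which lies close to the endpoint. The third-surgeon rule is not expressly extended to type.

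All of this is true as a description of the text. It shows a detail left unwritten; it does not show that any stated rule gives a wrong answer. The description in section 2.1 concerns what a fracture type can be treated with, not how a given reduction turned out.

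A raised false-positive rate needs more: the unblinded code would have to govern, and failures would have to be lost in one arm only. At assumed losses of 5% and 10% this gives 5.2% and 6.0%. The text suggests neither condition.

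The participant-flow diagram, introduced by "The following consort diagram will be continuously filled out to monitor study progress regarding primary outcome", is not available here and might show where other fracture types leave the primary analysis. No conclusion is drawn from its absence.

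**Conclusion.** The plan leaves unstated which record and which film define the Colles' set. This is a gap that competent readers and analysts fill sensibly: the blinded surgeons' typing governs, and the pre-reduction film is there for them to use. No stated figure is affected, and the 121 per arm reproduces. The secondary outcomes are evaluated for all included fractures (section 3.3) and do not depend on typing.

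If typing did respond to the result, equally in both arms, the test would stay valid and the odds ratio unchanged. At assumed rates up to 10%, the risk difference moves by less than 1 point and power falls by at most 3.4 points (80.2% to 76.8%). At 20% of successes the loss would be 7.5 points, but nothing in the documents points to relabelling at any rate. The conclusion rests on the surgeons' blinding in section 4.3 holding and on their typing, not the emergency department code, defining the set. No change to the plan follows.
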